### Study Size

30 patients will be treated on this study. Patients who enroll on study but withdrawal study consent or for any other reason never receive study therapy will be considered a screen failure and will be replaced. Additionally, in order to be considered eligible for the primary and secondary objectives described in this study, patients must receive (1) at least one dose of study therapy and remain on study until at least the first radiographic tumor assessment (week 6) or (2) at least one dose of study therapy and have clear clinical or radiographic progression prior to the planned first radiographic tumor assessment at week 6. Patients who come off study for reasons other than clinical/radiographic progression prior to the first radiographic tumor assessment will be replaced.

### **4.3 Rationale for dosage of nivolumab plus ipilimumab**

The dose and schedule of nivolumab in combination with ipilimumab in this proposed study is nivolumab 3 mg/kg every 2 weeks and ipilimumab 1mg/kg every 6 weeks. This dose and schedule selection was based on results of safety, efficacy, and exposure-response analyses obtained from the CA209-012 study (MSKCC IRB # 11-189).

### **4.5 Pre-treatment tumor resection or pre-treatment biopsy**

Pre-treatment tumor tissue will be obtained via surgical resection or biopsy from all patients enrolled on study. Tumor resections may be performed within 12 weeks (84 days) before beginning study therapy so long as there has been no intervening systemic anti-cancer therapy. Biopsies will be performed within the 28 day screening window.

Tumor resections will be standard-of-care. Possible indications may include a painful skin or lymph node metastasis or pleural effusions with pleural metastases which require resection and pleurodesis. However, if a standard-of-care tumor resection is not clinically indicated, patient may still fulfill pre-treatment tumor tissue requirements by having a biopsy which will be considered research non-billable unless otherwise indicated.

Initial processing of tissue from resection: In the case of those patients undergoing pre-treatment tumor resections, a portion of resected tumor tissue will be sent to pathology for diagnostic

confirmation of NSCLC and any other testing with may be required. A separate portion of tumor tissue (at least 1 x 1 x 1cm in aggregate size) will be collected from the OR or procedure room by a dedicated research assistant.

Resected tumor tissue will be delivered directly to the [name] Lab in ZRC15 and partitioned into at least three parts:

- One portion will be snap frozen for future DNA and RNA extraction.
- One portion will be processed as single-cell suspensions of tumor and infiltrating immune cells and then snap frozen for future T-cell assays.
- One portion will be processed as formalin-fixed tissue and will be embedded in paraffin for future IHC assays.

And if sufficient tissue is available:

- One portion will be processed fresh and infiltrating T-cells will also be isolated.

Initial processing of tissue from biopsy: In the case of those patients undergoing pre-treatment biopsies, image-guided core needle tumor biopsies are recommended.

Patient will undergo up to 5 core biopsies, if can be performed safely:

- Core #1 and #3 will be snap frozen for future DNA and RNA extraction.
- Core #2 will be placed in formalin, fixed, and embedded in paraffin.
- Core #4 and #5 (or more) will be processed either as snap frozen or as single-cell suspensions of tumor and infiltrating immune cells and then snap frozen for future antigen-specific T-cell assays.

If it is only possible to safely obtain fewer than five cores, priority will be given as numbered above.

A research assistant or investigator will be present at the time of the either resection or core biopsy to assess with material handling and processing.

Sufficient material must be collected to permit at least (1) frozen material for DNA/RNA extraction, and (2) FFPE material for IHC. Within 5 business days of each collected case, the adequacy of material collected with be reviewed and determination made regarding eligibility.

#### **4.6 On-treatment tumor biopsy**

On-treatment tumor tissue will be obtained from all patients enrolled on study on C2D8 (+/- 1 week).

Image-guided core needle tumor biopsies are recommended and the biopsied lesion is preferred not to be a target lesion.

Patients will undergo up to 5 core biopsies, if can be performed safely:

- Core #1 and #3 will be snap frozen for future DNA and RNA extraction.
- Core #2 will be placed in formalin, fixed, and embedded in paraffin.

- Core #4 and #5 (or more) will be processed either as snap frozen or as single-cell suspensions of tumor and infiltrating immune cells and then snap frozen for future antigen-specific T-cell assays.

If it is only possible to safely obtain fewer than five cores, priority will be given as numbered above.

A research assistant or investigator will be present at the time of the core biopsy to assess with material handling and processing.

#### **4.7 Tumor-based studies**

##### Tumor (and matched normal) whole exome and transcriptome sequencing for evaluation of mutational burden:

Tumor DNA, matched normal DNA, and tumor RNA will be extracted for whole exome and transcriptome analysis. Once DNA has been obtained and extracted, we will perform massively parallel sequencing of the whole exome of the tumor tissue and the available normal tissue. Genomic DNA will be captured via solution-based hybrid selection and sequenced on the Illumina HiSeq platform. Matched normal DNA will also be collected from whole blood and sequenced in conjunction with somatic tumor DNA. This is necessary to make variant calls in next-generation sequencing assays. It is not the intent of this analysis to utilize these samples to identify germline susceptibility mutations. However, in the course of investigating somatic sequence variations, germline susceptibility variants may be suggested by comparative germline sequencing. In addition, some somatic mutations are themselves directly suggestive of a germline predisposition (e.g. *BRCA1*).

The following plan will be followed by MSKCC investigators who identify a potentially actionable incidental finding in the course of research conducted on samples collected under this protocol:

In the event an investigator's research identifies a finding that he or she believes should be communicated to the subject (and/or family designee), the investigator shall communicate this to the OCR-IRB. The finding will be reviewed by a group convened by the IRB to determine whether the incidental finding should be discussed with the subject. In the event that group convened by the IRB determines that the finding should be discussed with the subject, and the subject has consented to be re-contacted, then the treating/consenting physician shall be contacted by the OCR-IRB representative and asked to refer the subject to the Clinical Genetics Service for further discussion of the research finding. After appropriate counseling and consent, the Clinical Genetics Service will request permission to confirm the result in a New York DOH-approved laboratory prior to communication of the specific result. If the patient is not available (e.g. deceased), then the surrogate designated on the consent will be contacted and the above will occur.

Germline BAM files will not be separately analyzed in the future without additional informed consent (such as responded YES to question 4 on the IRB# 06-107 consent form or consenting to IRB #12-245), anonymization, and/or human subjects review by this committee or the IRB.

The somatic sequencing data will be analyzed for base mutations, insertions, fusions, deletions, copy number alterations and in all target genes. Exon capture will be performed using the SureSelect

Human All Exon 50MB kit (Agilent). Enriched exome libraries will be sequenced on the HiSeq 2000 platform (Illumina) to >100X coverage. Raw sequencing data will be mapped to the human reference genome using the BurrowsWheeler Aligner (BWA). All filtered candidates will be annotated and manually reviewed (103) using the Integrated Genomic Viewer (IGV) (104). Mutations will be annotated using SnpEffect (105). In order to improve quality of calls in these FFPE samples, mutations will be analyzed using four callers: Somatic Sniper (106), VarScan (107), Strelka (108) and MuTect (109) then filtered by allelic frequency of each alteration in tumor (>10%) and normal (<3%), depth of coverage ( $\geq 7X$ ) and call quality. Calls made by only one caller will be manually reviewed using IGV (104).

Whole transcriptome tumor mRNA will be sequenced using next-generation sequencing. Briefly, after ribogreen quantification and quality control of Agilent BioAnalyzer (RIN>7), poly(A) RNA will be isolated using Dynabeads® mRNA DIRECT™ Micro Kit(Life Technologies) from 1ug of total RNA. mRNA is then fragmented using RNaseIII and purified. The Fragmented Samples quality and yield are evaluated using Agilent BioAnalyzer. Subsequently, the fragmented material will undergo Whole transcriptome Library preparation according to the Ion Total RNA-Seq Kit v2 protocol (Life Technologies), with 12 to 16 cycles of PCR. Samples will be barcoded, template-positive Ion PI™ Ion Sphere™ Particles (ISPs) will be prepared using the ion one touch system II and Ion PI™ Template OT2 200kit v2 Kit (Life Technologies). Enriched particles will be sequenced on a Proton sequencing system using 200bp version 2 chemistry. An average of 70 to 80 million reads will be generated per samples.

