### 6.2 Subject Inclusion Criteria

1. Patient must be capable, willing, and able to provide written, informed consent.
2.  $\geq 18$  years old.
3. Advanced stage NSCLC
4. Previously treated with no more than two lines of prior systemic therapy for advanced stage lung cancer.
  - a. Patients who previously received neoadjuvant, concurrent, or adjuvant chemotherapy for localized NSCLC and then recurred within 6 months of completing chemotherapy may be considered as having received one line of prior therapy
  - b. Maintenance therapy does not count as a separate line of therapy
5. Patients must:
  - a. Be scheduled to undergo a standard-of-care resection of tumor tissue as part of treatment plan prior to beginning study therapy OR have pre-treatment biopsy. Patients may not have intervening systemic anti-cancer therapy between the time of resection/biopsy and treatment with nivolumab.
  - b. Have collection of adequate pre-treatment tissue for correlative analysis defined as sufficient material for 1) frozen tissue for DNA/RNA extraction, 2) FFPE material for IHC. Adequacy of collected material will be determined within 5 business days of each collected case.
  - c. Have measurable by RECIST v1.1 (those undergoing pre-treatment resection must have imaging assessment after resection to determine measurability)
    - i. Previously irradiated sites of tumor may be considered measurable if there is radiographic progression at that site subsequent to the time of completing radiation.

- d. Have a safely biopsiable tumor lesion
6. ECOG performance status of 0-1.
7. Adequate hematologic, renal, and/or hepatic function (following criteria must be met within 28 days of C1D1):
  - a. WBC  $\geq$  2,000/ul
  - b. ANC  $\geq$  1,500/ul
  - c. Hemoglobin  $\geq$  9.0 g/dl
  - d. Platelet count  $\geq$  100,000/ul
  - e. Total bilirubin  $\leq$  1.5 x ULN (unless evidence of Gilbert's syndrome, in which case, direct bilirubin must be  $\leq$  1.0 x ULN)
  - f. AST and ALT  $\leq$  3 x UNL (unless elevated transaminases are felt to be directly related to metastatic disease involving the liver, in which case AST and ALT must be  $\leq$  5x ULN)
  - g. Serum creatinine  $\leq$  1.5 x ULN or estimated creatinine clearance of  $\geq$  40 mL/min calculated using the formula of Cockcroft and Gault:  $(140 - \text{Age}) \cdot \text{Mass (kg)} / (72 \cdot \text{creatinine mg/dL})$ ; multiply by 0.85 if female

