Primary objective 1: In each tumor sample, we will quantify the mutational burden (number of somatic, non-synonymous mutations detected through whole exome sequencing) and investigate graphically its relationship with response to nivolumab plus ipilimumab. We will describe the burden of mutations for responders and non-responders using summary statistics, and compare it (in an exploratory analysis) using Wilcoxon rank sum test. Depending on the number of responses, we may also perform logistic regression with mutational burden as a covariate and/or use Cox regression to analyze PFS and OS with mutational burden as a covariate. We expect that higher burden of somatic mutations will show an indication of positive association with response to nivolumab plus ipilimumab. Patients will be stratified into mutation “high” and “low” groups based on the median number of non-synonymous mutations/sample in patients with NSCLCs, and we will report objective response rate along with exact 95% confidence intervals in the low and high burden groups, respectively. Because this is not an established categorization, we will graphically

investigate whether other types of functional relationship between the burden of mutation and response might be more appropriate.

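### The fixed tumor allele-frequency filter makes the mutation count depend on sample purity, which the plan neither measures nor adjusts for

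*Combined protocol and SAP*

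**What the plan says.** Section 4.7 specifies exome libraries "sequenced on the HiSeq 2000 platform (Illumina) to >100X coverage", four variant callers, and calls "filtered by allelic frequency of each alteration in tumor (>10%) and normal (<3" (the last figure also in per cent), plus depth and call-quality limits. The same limits apply to every sample. The stated reason is "In order to improve quality of calls in these FFPE samples". Manual review covers candidates that survive filtering and calls found by a single caller. Nothing describes recovery of a call lost to the allele-frequency limit.

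Tissue adequacy is set out in section 4.5: "Sufficient material must be collected to permit at least (1) frozen material for DNA/RNA extraction, and (2) FFPE material for IHC". Inclusion criterion 5b in section 6.2 repeats this and adds: "Adequacy of collected material will be determined within 5 business days of each collected case". Neither gives a tumor-cell fraction. The pathology step in section 4.5 is diagnostic confirmation, described for resections, on a portion separate from the research tissue. Specimens may be resections or needle cores.

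Section 14.0 defines the burden for primary objective 1 as the "number of somatic, non-synonymous mutations detected through whole exome sequencing". That count enters the Wilcoxon comparison by response, the high/low split with exact confidence intervals, and the optional logistic and Cox models. Copy-number alterations will also be called (section 4.7), but not for the stated purpose of estimating purity.

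**The concern.** Allele frequency in a tumor sample reflects the share of tumor cells as well as the mutation itself. A fixed lower limit therefore removes more true mutations from a sample diluted with normal cells than from a pure one. Two tumors with the same burden can give different counts, and a low count may mean few mutations or few tumor cells.

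Primary objective 1 is the relation between burden and response. If purity is unrelated to response, the count is only noisier. If the two are related, for instance through immune infiltration or specimen type, the comparison mixes burden with sample composition. The study is meant to inform a larger one, so an unmeasured artifact could be carried forward. Candidate neoantigens are derived from the same calls.

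**Working it through.** **The plan's own figure.** The sample size of 30 rests on feasibility and budget, with no alpha, power or effect size, so there is no power figure to reproduce. The accrual arithmetic holds: 30 / 20 per year = 1.5 years = 18 months.

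**Retention.** Inputs from section 4.7 are the >10% limit and a depth of 100X, the stated minimum. For a clonal heterozygous mutation in a diploid region, expected allele frequency = purity / 2. The chance of passing is P(X ≥ 11), with X ~ Binomial(100, purity / 2). For a mutation in half of the tumor cells, the frequency is purity / 4.

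| Purity | Clonal kept | In half of tumor cells, kept |
|---|---|---|
| 15% | 13% | under 1% |
| 20% | 42% | 1% |
| 25% | 72% | 5% |
| 30% | 90% | 13% |
| 40% | 99% | 42% |
| 60% | about 100% | 90% |

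More depth does not cure this: at 20% purity, 43% of clonal mutations are kept at 150X.

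**Effect on the comparison.** From the documents: 30 patients and a response rate of about 30% (section 2.1), giving 9 responders and 21 non-responders. The effect size is the medians 299 versus 127 (section 3.0), which are detected counts by durable benefit on PD-1 monotherapy and serve only as an illustration. Assumed: log-normal burden with log SD 0.8 or 1.0, all mutations clonal, uniform purity ranges, and a two-sided Wilcoxon test at 0.05.

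| Assumed purity | Rejection rate, log SD 0.8 / 1.0 |
|---|---|
| True counts, no filter | about 69% / 50% |
| 15-60% in both groups | about 58% / 43% |
| Responders 15-40%, non-responders 30-60% | about 21% / 16% |
| Responders 30-60%, non-responders 15-40% | about 93% / 80% |
| No true association, either imbalance above | about 14-21% (nominal 5%) |

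A second set of assumptions points the same way. Here 20% of samples have purity 10-25%, the rest have 30-80%, and 20% of mutations are present in half of the tumor cells. With purity unrelated to response, power goes from 0.82 to 0.57 (log SD 0.7), from 0.58 to 0.43 (0.9) and from 0.44 to 0.32 (1.1). About 4 to 5 of 30 patients change side of the sample median, against about 1 with no low-purity samples. With no low-purity samples there is no power loss.

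**A purity floor as remedy.** With purity uniform on 15-60%, a 30% floor removes (30 − 15) / (60 − 15) = one third of patients, leaving about 6 versus 14. Power then falls further, from about 58% to 49% at log SD 0.8. With responders at 15-40%, 9 × (40 − 30) / (40 − 15) = 3.6 responders remain on average. The floor does remove the excess false positives.

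**The case against.** **The study is exploratory.** Section 14.0 calls the work descriptive, rules out definitive conclusions and expects later confirmation. No power is promised, so a loss of power breaks no guarantee. This stands, and it makes the point one of interpretability.

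**Purity may be adequate.** The documents give no purity distribution. Section 8.1 requires enough tumor tissue for the correlative work, and the case-by-case adequacy review could look at tumor content. The plan is silent on purity; it does not rule such a look out. This stands as a limit on size. Still, no purity value would reach the analysis.

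**The filter has a purpose.** It protects call quality in FFPE samples, and nothing here argues for dropping it. Section 4.5, however, assigns frozen material to DNA extraction, so the two sections should be reconciled.

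**Two stronger readings are tempting.** A reader might infer that the filter pushes the result toward the null, because responders' tumors would be more infiltrated and so less pure. Section 3.0 links PD-L1 expression with infiltrating lymphocytes and possible enrichment for response. But no section says that responders' samples are less pure, and the opposite imbalance inflates the association.

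A reader might also reckon that at 20% purity a burden of 299 reads as 0.417 × 299 = 125, much like the 127 of patients without durable benefit. Both medians are already counts detected by sequencing, and they are split by durable benefit, not by response. The likeness shows nothing about true burdens here.

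**Conclusion.** The point holds as a measurement problem of unknown size and direction. Followed as written, the plan yields counts that depend on purity below about 40% for clonal mutations, and at higher purity for subclonal ones. With purity unrelated to response, the cost under the 15-60% assumption is about 7 to 11 percentage points of power (50% to 43%, 69% to 58%). With purity related to response, the result can err either way. These figures rest on the assumed purity ranges, the assumed spread of burden and the borrowed effect size.

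The documents do not support saying that the primary association will be hidden, or that the exploratory design fails. This is a cheap improvement that would make either a positive or a null result easier to interpret.

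**What to change.** 1. Estimate purity for each sample from the exome and copy-number data already planned, blind to response.
2. Report purity by response group and plot burden against purity.
3. Keep the planned filter and count as the main result.
4. Prespecify one sensitivity analysis that repeats the Wilcoxon comparison and the high/low response rates with counts corrected for purity-dependent detection, for example the detected count divided by the pass probability at that purity. Alternatively, enter purity as a covariate in the optional logistic model, though two covariates with about 9 responders is thin.
5. Use a purity floor only as a secondary check, given the patients and power that it costs.

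The cost is some bioinformatic work, with no new tissue, visits or patients. Corrected counts will be noisy in very low-purity samples: at 15% purity the multiplier is 1 / 0.13, or nearly 8.

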#### Bioinformatic Analysis - identification of candidate neoantigens:

We have developed a bioinformatic pipeline to use whole exome sequencing to identify candidate neoantigens. Neoantigens are modeled *in silico* by examining the components of antigen presentation on MHC (*antigenicity*) (110). Expressed somatic missense mutations are translated into pairs of short peptide strings: one including the mutation and one corresponding to the wild-type sequence. Next, *in silico* analysis is performed using NetMHC (<http://www.cbs.dtu.dk/services/NetMHC-3.2/>) (111, 112)) or similar algorithm to predict the binding affinity of a given peptide for patient-specific MHC I. IEDB (<http://www.iedb.org>) (84)) can also be used to predict the induction of a T-cell response to a given amino acid peptide sequences or that have sequence homology to known antigens. Candidate neoantigens of particular interest will be identified by having predicted class I MHC binding affinity to patient-specific HLA alleles of at least 500nM.

The binding affinity of a given candidate neoantigen is dependant in part on the specific MHC I and II alleles that are presenting the antigen. Although initial studies restricted analysis to the predicted binding affinity to HLA-A\*02:01 (83), the most common allele in Caucasians, NetMHC 3.2 is now able to predict the nanomolar peptide binding affinity of nearly any human HLA allele (113). Exome sequencing done above may not provide sufficient coverage to accurately determine the patient-specific HLA allele, so HLA typing may be performed separately using normal DNA.

#### Co-stimulatory receptor and ligand expression:

FFPE tumor tissue collected from pre-treatment tumor resection and on-treatment biopsy will be examined for expression of PD-L1 on tumor and microenvironment cells by immunohistochemical (IHC) staining with the 28-8 antibody, and/or alternative method(s) if available. 3rd party vendors

have also developed IHC stains which may be used. In addition to PD-L1, there are other surface markers that may mediate immunogenicity and selective sensitivity to different immunotherapy approaches. These include, but are not limited to, MHC I, MHC II, PD-1, LAG-3, TIM-3 which can be examined by IHC, immunofluorescence, and/or flow cytometry.

